6.2 Administration

All subjects will be given 4 tubes of study drug and the same usage instructions. Subjects should spread a total of approximately 2 grams of study medication (using the dosing card) on both sides of the ankle. The study drug should be applied topically with the fingertips to both sides of the affected ankle for approximately 1 minute (corresponds to a region of approximately 200 cm²). After application, the hands should be washed. On Day 1, to demonstrate proper application, the first dose of study drug will be applied at the study center from the morning tube (regardless of the time of randomization). Subsequent doses will be applied from the tube associated with the corresponding time of day separated by at least 3 hours (i.e. if the first dose is applied at 15:00 hr from the morning tube, the next dose will be at approximately 18:00 hr from the late afternoon tube and the next dose will be applied on Day 1, if possible, preferably with at least 3 hours between doses.

The subjects will be instructed to continue to apply the gel topically with the fingertips four times a day for 7 days. Dosing times should be distributed as evenly as possible over the day, preferably once upon first arising (i.e., after washing or shower or bath), once at lunch (approximately 12:00 hour), once in the late afternoon (approximately 17:00 hour), and once in the late evening (i.e., after washing approximately 21:00 hour). There should be a period of at least 4 hours between individual applications. The appropriately-labeled tube should be used for each application.

Subjects can take a shower or bathe prior to application. Subjects should not shower, bathe or wash the treated area within the first three hours after the application. Subjects should wash their hands after use and should wait 10 minutes before covering the treated skin with clothing.

The investigator will instruct the subject to take the study drug exactly as prescribed and state that compliance is necessary for the subject's safety and the validity of the study. The subject will be told to contact the investigator if he/she is unable for any reason to take the gel as directed/prescribed. All dosages prescribed and dispensed to the subject and all dose changes during the study must be recorded on the Dosage Administration Record CRF. Any missed or skipped doses must be recorded in CRF.

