## 1.4 Sample Size Calculation

Approximately 300 subjects will be randomized to ensure at least 240 evaluable subjects complete the study for the Per Protocol (PP) analysis population. A maximum of 40 randomized subjects per center will be considered.

Approximately 120 subjects per treatment arm has been determined to provide 80% power to demonstrate non-inferiority of DDEA 2.32% gel b.i.d with DDEA 1.16% gel q.i.d. by comparing the two-sided 95% CI of the difference in mean change from baseline of VAS POM score between the two products with the non-inferiority margin of 13 mm. This assumes a treatment standard deviation of 22mm and allows for a possible small true treatment difference of 5mm in favor of DDEA 1.16%.

The margin of 13 mm (on a 100 mm VAS scale) was chosen as the literature reported minimally important clinical difference for an acute musculoskeletal injury (Todd et al 1995), with treatment differences smaller than 13mm considered as not clinically important. The standard deviation was obtained from a previous placebo-controlled ankle sprain study VOPO-P-307 with DDEA 2.32% gel.

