## 4.2.2 Protocol Deviations

Protocol deviations will be tracked by the study team throughout the conduct of the study. Data will be reviewed during Blinded Data Review Meeting (BDRM) prior to database lock to ensure all important deviations are captured and categorised.

Protocol deviations that would exclude subjects from PP population may include (but are not limited to) the following:

- Subjects failing to meet inclusion and exclusion criteria but are included in the study
- Subjects without a Day 5 POM VAS assessment
- Subjects with get application compliance <=80% or weight compliance <=65% or weight compliance >=143% or application compliance >=143% with study treatment.
- Subjects taking prohibited medication (Refer Appendix 4)
- Subjects identified with other major protocol deviations

GlaxoSmithKline Consumer Healthcare Confidential

Page 11 of 36

Full details of the major and minor protocol deviations are provided in Appendix 3.

The number and percentage of subjects with any major protocol deviations and with each type of major protocol deviations will be presented by treatment group (PPD ) using ITT population and listed in PPD . Any minor protocol deviations will also be listed similarly PPD .

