#### 4.4.1 Study Drug Compliance and Exposure

#### Compliance:

Compliance will be summarized descriptively based on the following points in PPD using ITT and Safety population respetively, PPD by ITT population on the following three :

- 1. % of scheduled applications made
- 2. % of gel used relative to number of actual applications \* 2g, and
- 3. compliance category (Good/Moderate/Poor).
- 1. % of scheduled applications made will be calculated in following way
  - a. % of scheduled applications compliance per tube:
  - Total number of applications made: Compliance will be summerized based on the percent of scheduled application made. Percent of scheduled application made for each dosing time morning, noon, late afternoon and late evening respectively will be calculated in the following manner.
  - If replacement kit number and replacement date (CRF: Study Medication Replacement) are missing -
    - $\circ$  Expected number of application from tube k=(number of applications per day from tube k) \* duration of days in the study ; where, k=1,2,3,4
    - Actual number of application from tube k= (Expected number of application)
       –[sum of (number of missed applications per day from tube k)\* duration of
       days gel is applied i.e. (Day i Day 1)]; where, i=1,2,3,4,5,6,7,8; k=1,2,3,4
    - Percent of scheduled application made from tube k= (Actual number of application from tube k ( where k=1 to 4) / Expected number of application from tube k) \*100.

GlaxoSmithKline Consumer Healthcare Confidential

Page 15 of 36

- If replacement kit number and replacement date (CRF: Study Medication Replacement) are non-missing then
  - Expected number of application from tube k=Sum of [ (number of applications per day from tube k from kit no. x) +(number of applications per day from tube k from kit no. y)\* duration of days in the study]; where x= Old kit # and y= New kit #, k=1,2,3,4
  - Actual number of application from tube k= (Expected number of application from tube k from kit no. x) –[sum of (number of missed applications per day from tube k from kit x)+ sum of (number of missed applications per day from tube k from kit y)]\* duration of days gel is applied i.e. (Day i Day 1)]; where, i=1,2,3,4,5,6,7,8; k=1,2,3,4; x= Old kit # and y= New kit #
- Percent of scheduled application made from tube k= (Actual number of application from tube k ( where k= 1 to 4) / Expected number of application from tube k) \*100% of scheduled applications compliance overall:

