  - Over all Compliance % = [sum of (actual # of application from each tube)/sum of (expected # of application from each tube)\*100]

Scheduled applications will include all scheduled applications through the day before the final visit. On day 1, the percentage of gel used will be calculated based on the possible number of administrations on that day. If only 3 were possible, then 100 % compliance on that day will be considered 3 applications.

- % of gel used relative to number of actual applications \* 2g will be derived as following -
  - Total weight of study medication used: The percent (%) of gel used will be computed relative to the actual number of application made from randomization through the final visit multiplied by 2 g.in two ways –
  - If replacement kit number and replacement date (CRF: Study Medication Replacement) are missing then
  - Expected weight of study medication used from tube k= (number of applications per day from tube k )\*2g \* Expected number of days gel to be applied from tube k
  - Actual weight of study medication used from tube k= [(Baseline weight of tube k (weight of tube k after last day of application ; k=1, 2, 3, 4

GlaxoSmithKline Consumer Healthcare Confidential Page 16 of 36

**Percent of total medication used** = (Actual weight of medication used/Expected weight of medication used)\*100

In case there is repeated usage of single tube in a day then the over usage of the medication will be reflected in weight compliance.

- Compliance category: Compliance category will be defined in the following way -
  - Good: > 80% of the gel has been applied and > 80% of scheduled applications made,
  - Moderate: not Good and not Poor
  - Poor: < 50% of the gel has been applied or < 50% of scheduled applications made.

For subjects applying active gel only twice per day (DDEA 2.32%), an additional compliance computation will be performed relative to the tubes and applications of active gel. If a subject is falls into good compliance category in both (separately for the active gel and also combined with placebo) then that subject will be included in the PP protocol population.

For each subjects time of the first application, application of the study drug each time point each day and the weight of the four tubes on Day 1, 3, 5 and 8 will be listed in **PPD** :

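### The SAP 4.4.1 application-compliance formula multiplies total missed doses by days, so if programmed as written one missed dose could remove a subject from the per-protocol set

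*SAP*

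**What the plan says.** - **Dosing and visits.** Protocol 6.2 has subjects "apply the gel topically with the fingertips four times a day for 7 days", which is at most 28 applications. Protocol 4.1 places the final visit at Day 8 ± 1.
- **Prose rule.** SAP 4.4.1 states that "Scheduled applications will include all scheduled applications through the day before the final visit". If only three applications were possible on Day 1, three count as full compliance for that day. Protocol 12.2.4.1 says the same.
- **Formula, no replacement kit.** For each tube, SAP 4.4.1 sets expected applications to the number per day times "duration of days in the study". Actual applications are expected minus a bracket that begins "sum of (number of missed applications per day from tube k" and is multiplied by the days gel was applied. Those days are described by Day i and Day 1, with i running from 1 to 8. The operator between the two is missing from the text as read; a minus sign is likely.
- **Formula, replacement kit.** Expected adds terms for the old kit (x) and the new kit (y). Actual starts from the expected number for kit x only and then subtracts the misses from both kits.
- **Use.** SAP 4.2.2 lists as a PP exclusion "Subjects with get application compliance <=80% or weight compliance <=65"%, and SAP 4.2.3 requires application compliance above 80%. SAP 4.5.1.2 runs the primary analysis on PP without imputation. For DDEA 2.32% subjects, SAP 4.4.1 adds a calculation on the active tubes alone and links PP inclusion to good compliance on both that and the combined figure.

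**The concern.** Missed applications summed over the days of use are already the total missed. Multiplying that sum by days again inflates each miss several-fold, and the result is compared with a cut-off that decides who enters the primary analysis.

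The expected count also has two definitions: the prose gives an end point and a Day 1 adjustment, and the formula gives neither. Protocol 6.2 makes Day 1 matter, because its own example of a 15:00 first dose moves from the morning tube to the late afternoon tube and leaves the noon tube unused at that point.

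At stake are the membership of the PP set, the 240 evaluable subjects on which the power statement rests, and possibly balance between arms, since only DDEA 2.32% subjects have the extra active-tube calculation. SAP section 5 shows that PP membership is sensitive to compliance rules: it reports that most subjects had weight compliance between 50% and 80% and gives that as the reason for revisiting the PP definition.

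**Working it through.** **1. The plan's sample size.** Inputs from SAP 1.4: "Approximately 120 subjects per treatment arm has been determined to provide 80% power", a "non-inferiority margin of 13 mm", SD 22 mm, a true difference of 5 mm in favour of DDEA 1.16%, and a two-sided 95% CI.

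n per arm = 2 × (1.960 + 0.842)² × 22² / (13 − 5)² ≈ 119, against the stated 120. Power at 120 per arm is 80.4%. The allowance 300 × 0.8 = 240 also agrees. The SAP gives no worked compliance figure to reproduce.

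**2. The missed-dose term.** Take one application missed out of 28, so true compliance is 27/28 = 96.4%. Overall compliance is the sum of actual over the sum of expected across the four tubes.

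| Reading of the term | Calculation | Result | Against 80% |
|---|---|---|---|
| Sum × days, 7 expected days, multiplier 7 | (28 − 7)/28 | 75.0% | excluded |
| Sum × days, 8 expected days, multiplier 7 | (32 − 7)/32 | 78.1% | excluded |
| Sum × days, 7 expected days, multiplier 6 | (28 − 6)/28 | 78.6% | excluded |
| Each miss × (its day − 1), 7 expected days | from 28/28 to (28 − 6)/28 | 100% to 78.6% | excluded only for a Day 7 miss |
| Average daily rate × days | (28 − (1/7) × 7)/28 | 96.4% | kept |

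Only the last reading returns the true value.

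**3. Active tubes alone (DDEA 2.32%).** Two applications a day for 7 days is 14. One miss with multiplier 7 gives (14 − 7)/14 = 50.0%, against a true 13/14 = 92.9%.

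**4. Day 1.** If three applications were possible and all later ones were made, the prose gives 27/27 = 100%. Under the formula, if the impossible application is recorded as missed, the score is 27/28 = 96.4% without the multiplier and (28 − 7)/28 = 75.0% with it.

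**5. Replacement kit, no missed dose, one application per tube per day over 7 days.** The grouping of terms is unclear, so several readings were tried for one tube:
- Expected 1 + 1 × 7 = 8, actual from kit x = 1: 12.5%.
- Expected (1 + 1) × 7 = 14, actual from kit x = 7: 50.0%.
- Expected 8, actual from kit x = 7: 87.5%.
- Expected 7, with kit x used for 3 days and kit y for 4 (an assumed split), actual = 3: 42.9%.

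The correct value is 100%. Three of the four fall at or below 80%.

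**6. Sensitivity of power to PP size.** The sizes are assumptions, since no missed-dose rate is given: 110 per arm gives 76.9%, 100 gives 73.0% and 80 gives 63.3%.

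**The case against.** The missed-dose term has a valid reading. If missed applications per day is a rate, rate times days equals the total and the formula is correct. The text has also lost an operator at this point. A literal multiplication soon produces impossible values (two misses from one tube give 7 − 14 = −7 applications), which a programmer should notice. The listed PP exclusions are ones that may apply, and assignment passes through the blinded data review meeting. The primary endpoint is also analysed on mITT and ITT, which do not depend on compliance.

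Much of this stands, and it makes the result conditional on how the formula is programmed. It does not remove the defect. The wording is a sum of numbers, not a rate, and restoring a minus sign does not remove the multiplication. A single miss yields a plausible 75%, which would not stand out. The review meeting applies definitions but does not supply the formula, and the other analysis sets do not repair the one named as primary.

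A reader might infer that a subject who applied all 28 doses is excluded when the final visit is late. The documents do not support this. Dosing is scheduled for 7 days, so a Day 9 visit naturally still gives 28. Even if an undosed Day 8 is counted, the prose rule gives 28/32 = 87.5%. A Day 7 visit gives at most 28/24 = 116.7%, below the 143% limit. In the formula without a replacement kit, actual is found by subtraction, so a subject with no recorded miss scores 100% whatever duration is used.

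**Conclusion.** The formula is wrong as written. If the missed-dose term is programmed as a sum times days over the whole period, one missed application turns a true 96.4% into 75.0% to 78.6% (50.0% on the active tubes) and could drop the subject from PP. The application cut-off is 80% both in SAP 4.2.2 and in the good-compliance category, so this does not turn on which PP rule governs.

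The expected count is undefined and conflicts with the prose on Day 1. The replacement-kit formula can fail even a subject who missed nothing, on most readings tried.

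The figures assume four applications a day for 7 days and one recorded miss. The documents give neither a missed-dose rate nor a number of kit replacements, so the number wrongly excluded and the loss of power cannot be computed. It would be too strong to say that compliant subjects will be excluded: they could be, under the literal programming.

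**What to change.** Rewrite the application-compliance derivation in SAP 4.4.1:

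1. Expected applications are those scheduled within the protocol's 7-day dosing period, through the day before the final visit or through discontinuation if earlier, minus those not possible on Day 1. With all four possible on Day 1, this gives 24 for a Day 7 visit and 28 for Day 8 or Day 9. A flat 28 would penalise a Day 7 visit, when product is collected before the seventh day is complete: a full doser would score 24/28 = 85.7%.
2. Actual applications are expected minus the total number missed, with no multiplication by days.
3. Each tube has one expected and one actual count across original and replacement kits.

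With 28 expected, one miss gives 27/28 = 96.4% and five give 23/28 = 82.1% (both kept); six give 22/28 = 78.6% (excluded).

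The cost is SAP wording and a derivation correction before database lock. No new data are needed: Protocol 6.2 already requires missed doses in the CRF, and Protocol 6.8 has the diary record each application.

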Subjects will be instructed not to remove study products from the opaque bags provided outside of the dispensing room, while at the study site. Dispensing staff and staff supervising administration of IP will not be involved in any efficacy/safety assessment procedures during the study.

Randomization data will be kept strictly confidential, accessible only to authorized persons, until the time of unblinding. After the study is completed, the data file verified, and protocol violations determined, drug codes will be broken and made available for data analysis.

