12.2.1 Definition of Analysis Populations

The safety population will include all subjects who are randomized and have received at least one dose of investigational product.

The modified intent-to-treat (mITT) population will consist of all randomized subjects who have at least one post baseline POM VAS assessment

The PP population includes all subjects from the mITT population who do not have any major protocol deviations that could confound the interpretation of the efficacy analyses. Protocol deviations that would exclude subjects from the PP population are defined in Section 12.2.2.

Before the study is unblinded, each actual post-baseline visit will be mapped to the target visit date to which it is chronologically closest. This corresponds to the following visit windows: Visit 2 (Days 2–4), Visit 3 (Days 4–6), Visit 4 (Days 7+). The numbering of the actual visits (from Visit 1 to Visit 4) will then be changed as needed to improve the correspondence of the actual visit dates to the protocol-specified schedule of visits, particularly in relation to Visit 3 (primary). Final determinations will also be made and documented before the study is unblinded to address visits that occur on Day 4 (which maps to two visit windows) or visits occurring well beyond the target date for the final visit or any other irregularities. Further detail is provided in the statistical analysis plan.

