12.2.4 Study Drug/Product Compliance and Use of Other Therapies

12.2.4.1 Study Drug/Product Compliance

Compliance is defined in terms of the total weight of study medication used and total number of applications made as follows:

- Good: > 80% of the gel has been applied and > 80% of scheduled applications made,
- Moderate: not Good and not Poor
- Poor: < 50% of the gel has been applied or < 50% of scheduled applications made.

The % of gel used will be computed relative to the actual number of applications made from randomization through the final visit multiplied by 2 g. This value is to be recorded in the CRF. Scheduled applications will include all scheduled applications through the day before the final visit. On day 1, the percentage of gel used will be calculated based on the possible number of administrations on that day. If only 3 were possible, then 100 % compliance on that day will be considered 3 applications.

Compliance will be summarized descriptively as (1) % of scheduled applications made, (2) % of gel used relative to number of actual applications * 2g, and (3) compliance category (Good/Moderate/Poor). Exposure to study drug will be summarized descriptively as (1) number of applications made and (2) total amount of gel used.

For subjects applying active gel only twice per day (DDEA 2.32%), and additional compliance and exposure computation will be performed relative to the tubes and applications of active gel.

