## **Document History**

| Document | Version Date | Summary of Changes (New analysis or Change in planned analysis)          |
|----------|--------------|--|
| 0.1      | 02FEB2020    | Not Applicable   |
| 0.2      | 03SEP2020    | Updated client comments received on Draft 1 and added COVID-19 analysis. |
| 1.0      | 11JAN2021    | Updated Per Protocol definition.   |
|          |              | Made changes to PP exclusion reason w.r.t compliance category.           |
|          |              | Added sensitivity analysis for primary endpoint.                         |
| 2.0      | 20JAN2021    | Made changes to PP exclusion reason w.r.t compliance category.           |

Amendments incorporate all revisions to date.

GlaxoSmithKline Consumer Healthcare Confidential Page **3** of **36** 

211206

Statistical Reporting and Analysis plan Draft V2.0 20JAN2021

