#### 4.2.3 Analysis Populations

There are five analysis populations defined as below:

GlaxoSmithKline Consumer Healthcare Confidential Page 12 of 36

211206

Statistical Reporting and Analysis plan Draft V2.0 20JAN2021

| Table 4-1                           | Analysis Population  |  |   |
|-------------------------------------|--|--|---|
| Population                          | Definition / Criteria  | Analyses
Evaluated  | Treatment
s to used
for
Analyses |
| Enrolled                            | Comprise of all the subjects who have signed ICF,
though may or may not be randomized later into the
study.  | Disposition  |   |
| Intent-To-
Treat
(Randomised) | Comprise of all randomized subjects.
This population will be based on the treatment to which
the subject was randomized.
Any subject who receives a treatment randomization
number will be considered to have been randomized.   | Efficacy
Demographics/Di
sposition/Medical
History/Concomit
ant
Mediaction/Comp
liance | Planned
treatment
received          |
| Safety                              | Comprise of all subjects who receive at least one dose
of study treatment.
This population will be based on the treatment the
subject actually received.  | Study Population
Safety   | Actual
treatment
received           |
| Intent-To-
Treat
(Modified)   | Comprise of all randomized subjects who have at least one post baseline POM VAS assessment.  | Efficacy
Demographics   | Planned
treatment
received          |
| Per-Protocol
(PP)                | All subjects from the mITT population who do not have
any major protocol deviations (which are not affecting
primary efficacy endpoint) and also weight
compliance > 65% and application compliance >
80%that could confound the interpretation of the
efficacy analyses.
Protocol deviations that would exclude subjects from
the PP population will be discussed in the BDRM. | Primary Efficacy
Demographics.  | Actual
treatment
received           |

Table 4-1Analysis Population

The numbers of subjects included in each of the analysis populations, and the number excluded from each population broken down by the reason for exclusion will be presented (PPD) using enrolled population. Subjects excluded from any of the analysis populations will be listed in PPD, with the reason for exclusion.

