#### 4.5.1.2 Statistical Hypothesis, Model, and Method of Analysis

The hypothesis of the study is stated below:

H0: The Diclofenac 2.32% DDEA Gel administered BID is inferior to Diclofenac1.16% DDEA gel administered QID.

 $\mu_T \text{-} \mu_S \geq \delta$ 

Where,  $\mu_S$  is the mean for a standard therapy (Diclofenac 1.16% DDEA Gel administered QID) and  $\mu$ T is the mean for test therapy (Diclofenac 2.32% DDEA Gel administered BID).  $\delta$  is the non-inferiority margin of 13 mm.

H1: Diclofenac 2.32% DDEA Gel administered BID is non-inferior to Diclofenac 1.16% DDEA gel administered QID.

 $\mu_T \text{ - } \mu_s < \delta$ 

 $\delta = 13 \text{mm}$ 

The primary efficacy analysis will be performed on PP population without imputation of missing data. The primary endpoint (Change from baseline in POM ) will be analysed using

GlaxoSmithKline Consumer Healthcare Confidential

Page **19** of **36** 

211206

Statistical Reporting and Analysis plan Draft V2.0 20JAN2021

Analysis of Covariance (ANCOVA) model with treatment and center as factors and baseline POM as covariate.

Diclofenac 2.32% DDEA Gel administered BID will be declared non-inferior to Diclofenac 1.16% DDEA gel administered QID if the upper limit of the two-sided 95% confidence interval of the difference between their mean changes from baseline VAS POM responses is less than the established margin of 13 mm.

Refer sample SAS code in APPENDIX 4.

Assumptions of normality and homogeneity of variances in the ANCOVA model will be evaluated after study un-blinding. If violations are observed then the following will be performed as a post-hoc sensitivity analysis and results will be compared with primary analysis results:

- 1. Suitable data transformations will be tried to achieve the assumptions.
- 2. If suitable transformations cannot be found, then the non-parametric Van Elteren tests will be performed using center as strata. Two sided 95% CI and p value will be presented.

POM by 100 mm VAS analogue scale (CRF page: Pain on Movement ; variable VASSCRL)will be summarized over time (**PPD**) using mITT population. Also POM by 100 mmVAS analogue scale will be summerarized over time by center using mITT population (**PPD**). Above tables (**PPD**) will be repeated for the PP population. POM by 100 mm VAS analogue scale for COVID 19 patients if any will be summarized in **PPD** using mITT population.

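### The SAP's compliance rules for its primary per-protocol set disagree: a sentence in 4.4.1 and the wording of Table 4-1 do not match the limits in 4.2.2

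*SAP*

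**What the plan says.** SAP 4.5.1.2 makes PP the primary set: "The primary efficacy analysis will be performed on PP population without imputation of missing data". Three parts of the SAP bear on who is in it.

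- **SAP 4.2.2** lists among the PP exclusions: "Subjects with get application compliance <=80% or weight compliance <=65% or weight compliance >=143% or application compliance >=143% with study treatment". Table 3 in section 5 repeats these limits as a declared change from the protocol, which had excluded Poor and Moderate compliance (protocol 12.2.2).
- **SAP 4.4.1** defines Good as more than 80% of gel and more than 80% of scheduled applications. It adds a separate active-gel computation for DDEA 2.32% subjects, and then says: "If a subject is falls into good compliance category in both (separately for the active gel and also combined with placebo"), the subject will be in PP.
- **SAP 4.2.3, Table 4-1** defines PP by weight compliance above 65% and application compliance above 80%, with no upper limit. It requires that subjects do not have "any major protocol deviations (which are not affecting" the primary endpoint. Protocol 12.2.1 instead takes mITT subjects "who do not have any major protocol deviations that could confound the interpretation of the efficacy analyses".

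Protocol 12.2.4.1 introduces the active-gel calculation as an "additional compliance and exposure computation will be performed relative to the tubes and applications of active gel" and does not make it a PP criterion. On timing, protocol 6.5 says that once the study is completed, the data file verified and "protocol violations determined, drug codes will be broken and made available for data analysis". Protocol 12.2.2 and SAP 4.2.2 place the exclusion decisions at a blinded review meeting before database lock.

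**The concern.** Membership of the primary non-inferiority set should follow from one written rule that can be applied without the treatment code. Here a programmer who works from 4.4.1 and one who works from 4.2.2 can build different sets from the same data. One element of 4.4.1 cannot be evaluated while the study is blind. The primary result, the PP versions of the secondary analyses, and the supportive analyses on PP all depend on this set.

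**Working it through.** No figure in the plan is in dispute. The sample size in SAP 1.4 reproduces: n per arm = 2 × 22² × (1.96 + 0.842)² / (13 − 5)² ≈ 119, against about 120 stated. The check is to apply each rule to the same subjects.

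**1. Thresholds.** Inputs are the limits in SAP 4.2.2, Table 4-1 and 4.4.1. The subjects are hypothetical, have no other deviation, and all have 95% application compliance. Only weight is varied, because 4.4.1 counts applications as expected minus missed and says that over-use shows up in weight.

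| Weight | 4.2.2 | Table 4-1 limits | Good in 4.4.1 | 4.4.1 sentence, literal | 4.4.1 sentence, as a requirement |
|---|---|---|---|---|---|
| 90% | in | in | yes | in | in |
| 70% | in | in | no | silent | out |
| 60% | out | out | no | silent | out |
| 150% | out | in | yes | in | not barred |

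- At 150%, 4.2.2 excludes the subject and 4.4.1 includes them. This conflict needs no interpretation of the sentence.
- At 70%, there is a conflict only if the sentence is read as a requirement, as under the protocol's exclusion of Poor and Moderate.
- At or below 65%, both rules exclude, so nothing changes.

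**2. Active-gel check.** Four applications a day for 7 days give 28 scheduled, of which 14 come from the morning and late-afternoon tubes (this assumes four were possible on Day 1). Take a record with three misses, all from those two tubes, and weight compliance above 80%.

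- All tubes: 25/28 = 89.3%, which is above 80%.
- Morning and late-afternoon tubes: 11/14 = 78.6%, which is not.

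If the record belongs to a DDEA 2.32% subject, active-gel compliance is 78.6% and the check fails. If it belongs to a DDEA 1.16% subject, every tube is active, active-gel compliance is the same 89.3%, and the check is redundant. The outcome therefore cannot be settled until the arm is known. That is out of order with protocol 6.5 and 12.2.2 and SAP 4.2.2.

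**3. Table 4-1.** The parenthesis disqualifies for deviations that do not affect the primary endpoint. The same cell goes on to refer to confounding of the efficacy analyses, as protocol 12.2.1 does. The two halves of the cell point in opposite directions.

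**4. Which rule is current.** The document history lists an updated PP definition in version 1.0, and under both 1.0 and 2.0 it has "Made changes to PP exclusion reason w.r.t compliance category". Section 5 gives the new limits and does not mention the 4.4.1 sentence. That the sentence is a remnant of the protocol's Good-only rule is an inference, but it fits this history.

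**The case against.** The strongest reply is that section 5 and 4.2.2 already make the intended rule clear, and that the rest is untidy drafting. Much of this stands.

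- The 4.4.1 sentence says if, not only if. Literally it drops nobody with weight compliance between 65% and 80%. The literal conflict is confined to Good subjects at or above the cap.
- Section 5 records the cap as an other deviation, so it could reach Table 4-1 through the major-deviation clause and the blinded review meeting. The table's silence is an omission more than a flat contradiction.
- The Table 4-1 cell keeps the confounding test, so a reader who infers that only harmless deviations are disqualifying goes further than the text.
- The overall formulas in 4.4.1 sum over the tubes, which largely supplies an all-tube basis for the limits.
- The boundary of at least 80% in SAP 4.5.1.3 is expressly for that sensitivity analysis and is not counted here as a conflict.

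Two stronger readings are tempting. The first is that the active-gel check treats equal behaviour unequally and so biases the comparison. The documents do not support this: three missed active applications are 3/14 = 21.4% of active doses for DDEA 2.32% and 3/28 = 10.7% for DDEA 1.16%. What remains is the need for the treatment code. The second is that PP would shrink and lose power, because section 5 reports that most subjects had weight compliance of 50% to 80%. That would cost a Good-only rule which section 5 shows is no longer intended, and the documents do not say how many of those subjects lie above 65%.

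The reply does not remove the 4.4.1 sentence, which conflicts with 4.2.2 on either reading and cannot be applied blind.

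**Conclusion.** The point holds as an alignment error that should be fixed, not as an open choice between rules. Stated rules that contradict one another bear on who enters the primary non-inferiority analysis. The conflict with the cap follows from the text alone. The conflict for weight above 65% and up to 80% rests on reading 4.4.1 as a requirement. The blinding problem arises only if the active-gel check is used for PP membership.

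The size cannot be given, because the documents do not report how many subjects change status. No power loss and no bias in the treatment difference is claimed. The mITT analyses (protocol 12.2.5, SAP 4.5.1.2) and the ITT analyses (SAP 4.5.1.3) do not depend on these rules.

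**What to change.** Before unblinding:

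1. Delete the 4.4.1 sentence on PP inclusion. Keep the active-gel computation as descriptive, as in protocol 12.2.4.1.
2. In Table 4-1, state the 4.2.2 limits including the 143% cap, or refer to 4.2.2.
3. Correct the Table 4-1 parenthesis so that it refers to deviations that do affect the primary efficacy endpoint.
4. Confirm in 4.2.2 that the limits use the overall, all-tube compliance already defined in 4.4.1, in both arms.

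The cost is SAP wording only. No new data are needed, and no sample size or analysis model changes. SAP 2.2 places finalization and signature of the plan ahead of database lock and unblinding, which is the natural point to make these edits.
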